7.1. Selection Criteria

The table on the following pages outlines the specific inclusion and exclusion criteria for the study. Before randomization in the study, a patient must meet all of the inclusion and exclusion criteria.

Inclusion Criteria:	
1.	Age 18-80years
2.	Dependent upon daily PPIs for > 6 months. Daily use is defined as a double dose, or full dose or half dose taken daily for more than 80 % of the total number of days during the proceeding evaluation period
3.	Troublesome symptoms, specifically heartburn or regurgitation, while on optimized dose of PPI's. Troublesome heartburn or regurgitation symptoms are those which occur a minimum of 2 days a week and are mild to severe in severity.
4.	Abnormal ambulatory (Bravo) pH study after off PPI therapy for 7 days, i.e. >5.3% of the time with pH < 4 in a 48-hour monitoring period
5.	Normal or near normal esophageal motility (by Upper GI/ esophagram or manometry as required)
6.	Pre-enrollment Hiatal Hernia (axial height and transverse dimension) from > 2cm and up to 4 cm inclusive
7.	Patient willing to cooperate with post-procedure dietary recommendations and assessment tests at the requisite follow-up visits
8.	Signed informed consent
Pre-enrollment Exclusion Criteria:	
1.	BMI > 35
2.	Hiatal hernia \leq 2 and > 4 cm
3.	Esophagitis Los Angeles grade C or D
4.	Esophageal ulcer
5.	Esophageal stricture
6.	Long-segment Barretts esophagus (Prague: C > 1, M > 3)
7.	Esophageal motility disorder
8.	Pregnancy or plans for pregnancy in the next 12 months (in females)
9.	Immunosuppression
10.	ASA > 2
11.	Portal hypertension and/or varices
12.	History of previous resective gastric or esophageal surgery, cervical spine fusion, Zenker's diverticulum, esophageal epiphrenic diverticulum, achalasia, scleroderma or dermatomyositis, eosinophilic esophagitis, or cirrhosis
13.	Active gastro-duodenal ulcer disease
14.	Gastric outlet obstruction or stenosis
15.	Severe gastroparesis or delayed gastric emptying confirmed by solid-phase gastric emptying study if patient complains of postprandial satiety during assessment
16.	Coagulation disorders
17.	Symptoms including gas bloat and dysphagia.
18.	Any other presenting condition that in the opinion of the investigator would not make participation in this study in the patients best interest.
Post-enrollment Exclusion Criteria:	
1.	Inability to repair Hiatal hernia with at least 2cm of intra-abdominal esophagus length.

7.2. *Withdrawal*

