While study withdrawal is discouraged, patients may withdraw from the study at any time, with or without reason and without prejudice to further treatment. Withdrawn patients will not undergo any additional follow-up. In all cases of withdrawal, the reason(s) for withdrawal (if given) will be recorded upon study termination.

8. Study Methods and Techniques

8.1. *Clinical Symptom Assessments*

The following four GERD-specific questionnaires will be used to assess typical and atypical symptoms, their frequency and intensity, as well as their impact on daily life, relationships, quality of life, state of mind, worries and concerns, sleep and diet.

- Reflux Disease Questionnaire (RDQ)
- GERD HRQL Quality of life assessment
- GERD GSRS Quality of life assessment
- RSI Questionnaire for atypical symptoms

- The time needed for completion of all four questionnaires is estimated for 35 minutes maximum.
- A $\geq 50\%$ improvement in the total GERD-HRQL and GERD-GSRS scores compared to the baseline off PPIs will be considered clinically significant.
- A reduction in severity from \geq moderate to \leq mild and/or a reduction in frequency from ≥ 2 days per week to ≤ 1 day per week is indicative of a clinically significant result as measured by the Reflux Disease Questionnaire (RDQ).

8.2. *PPI Usage*

The use of PPIs plus other GERD medication such as histamine receptor antagonists (H2RA) and antacids will be recorded in a medication diary using generic names (**Table 3**) and classified according to the daily dose and frequency.^{18, 21}

Usage will be defined as “Daily” if a double dose, full dose or half dose is taken daily for more than 80% of the total number of days during the proceeding follow-up period.

Note: “Full Dose” is defined as the first number of mg listed for each PPI in the following table.

Table 3. Proton Pump Inhibitors (PPI)

Generic Name	Brand Names	Available Pill Sizes (mg)
Esomeprazole	Nexium	20, 40
Lansomeprazole	Prevacid, Dakar, Lando, Lanzor, Prezal, Lanzol	15, 30
Omeprazole	Prilosec, Losec, Logastric	10, 20, 40
Pantoprazole	Protonix, Zurcal, Pantozol, Zurcale	20, 40
Rabeprazole	Aciphex, Pariet	20

8.3. *Upper GI Endoscopy*

- Diagnosis of esophagitis according to the Los Angeles classification confirmed by esophageal biopsy.²²
- Hiatal hernia size will be diagnosed based on the distance from Z-line to diaphragmatic impression measured in cm at retraction of the endoscope without insufflation.

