The following pre-procedure data must be collected in order to determine eligibility:

- Informed consent signing
- Physical Examination
- Days since last PPI intake (prior to BRAVO pH study)
- EGD with optional biopsy
- High resolution motility studies (optional)
- Upper GI endoscopy
- Bravo pH studies (48 hours)

Patients who have met all entry criteria are enrolled to the study.

9.2. *Prior to the Study Procedure*

- The usage of any anticoagulants will be discontinued before TIF for at least 10 days.
- 12-hours before the procedure, the patient is expected to be fasting.
- Immediately before the procedure, each patient will undergo an endoscopic examination of the stomach and esophagus.

9.3. *During the Study Procedure*

A Transoral Incisionless Fundoplication will be performed following the standard laparoscopic Hiatal Hernia Repair and closure of the diaphragmatic defect (crura closure will be made

posterior with 2-3 separate stitches). The patient will be terminated from the study if hiatal hernia cannot be repaired, with at least 2 cm intra-abdominal esophageal length.

TIF Procedure (Treatment)

The TIF procedure (treatment) will be conducted under continuous visualization following a standard TIF2.0 protocol (**Figures 8**).

[figure not shown]

Figure 8. Standard TIF2 protocol

The usage of any anticoagulants will be discontinued before HHR and TIF 2.0 for at least 10 days. Patients are expected to fast for 12 hours before the procedure. Antibiotic prophylaxis will be administered during induction of general anesthesia (oro-tracheal intubation and anti-emetic protocol; dehydrobenzoperidol, dexamethasone, Zofran, Primperan).

As stated in Section 10.2, immediately before the procedure, each patient will undergo an endoscopic examination of the stomach and esophagus. The EsophyX ZR will be inserted transorally through a bite-block into the esophagus with the patient in either in supine, or 45 degrees or left lateral position.

During a single insertion of the device, a valve similar to that created through antireflux surgery will be reconstructed by retraction of full-thickness plications and tailored placement of multiple fasteners circumferentially 1-3 cm above the Z-line. The procedure is expected to last for 30-45 minutes. The quality of the

created valve will be evaluated by an endoscopic examination immediately after the procedure. Any complications related to the procedure will be recorded.

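### Axial hernia size is measured from the Z-line, which sits too high in the shorter-segment Barrett's that remains eligible, so the axial reading against the >2 to 4 cm window can be too large

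*Combined protocol and SAP*

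**What the plan says.** Section 8.3 (Upper GI Endoscopy) contains the only sizing method in the protocol: "Hiatal hernia size will be diagnosed based on the distance from Z-line to diaphragmatic impression measured in cm". This is an axial distance.

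Section 7.1 makes hernia size decide eligibility. Inclusion 6 reads "Pre-enrollment Hiatal Hernia (axial height and transverse dimension) from > 2cm and up to 4 cm inclusive", and exclusion 2 reads "Hiatal hernia \leq 2 and > 4 cm". Inclusion 6 therefore asks for two dimensions, while 8.3 gives a method for one.

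Exclusion 6 in the same section concerns "Long-segment Barretts esophagus (Prague: C > 1, M > 3"). Shorter segments are not excluded. The text does not say whether the C and M limits are joined by *and* or by *or*.

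Nothing later in the plan catches a mis-sized hernia. Section 9.2 says "Immediately before the procedure, each patient will undergo an endoscopic examination of the stomach and esophagus", but attaches no re-measurement and no size-based action. The one post-enrollment exclusion in 7.1 is "Inability to repair Hiatal hernia with at least 2cm of intra-abdominal esophagus length". Under section 9.3, enrolled patients have a laparoscopic repair and then the TIF procedure.

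**The concern.** The Z-line is the junction between squamous and columnar mucosa. Barrett's esophagus means columnar lining above the gastroesophageal junction, so a circumferential segment raises the Z-line by its own length. This follows from the meaning of the term; the protocol does not state it. In such a patient the 8.3 distance is the axial hernia length plus the columnar segment, and the rule as written gives a wrong axial size.

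The eligibility window is only 2 cm wide, so a shift of 0.5 to 1 cm is a quarter to a half of it. The lower edge also matters to the research question. Section 1 describes the study as exploring TIF after hernias of >2 to 4 cm have been reduced, and sets the results against those of patients who present with hernias of 2 cm or less. An axial over-reading can bring a patient from the second group into the first and lead to a laparoscopic repair outside the stated target. At the upper edge it can turn away patients the study wants.

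**Working it through.** **The plan's own figure.** Sections 10.2.2 and 10.1 (Sample Size and Power Estimation) use N = 50, a null rate of 24%, an assumed rate of 44%, one-sided 0.05, and success at 18 or more normalized. Exact binomial:

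- P(X ≥ 18 | 50, 0.24) = 0.0384, and P(X ≥ 17 | 50, 0.24) = 0.0718, so 18 is the smallest valid cut-off.
- P(X ≥ 18 | 50, 0.44) = 0.901, against the stated 0.90.

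These figures reproduce and do not depend on how hernias are sized.

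**Inputs for the sizing question**

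- Window: >2 to 4 cm (7.1, inclusion 6 and exclusion 2).
- Landmark: Z-line (8.3).
- Permitted circumferential length: up to 1 cm if C above 1 is enough to exclude (7.1, exclusion 6). If C and M must both exceed their limits, a segment such as C2 M3 is also permitted and the shift could be larger.
- Barrett's prevalence, segment length and distribution of true hernia size: not in the documents, so assumed below.

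**Model.** Axial reading = true axial height + s, where s is the upward displacement of the Z-line. The axial criterion is met if the reading is >2 and ≤4 cm.

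| s | True axial height that reads >2 to 4 cm | Of these, truly ≤2 cm | True >2 to 4 cm that reads >4 cm |
|---|---|---|---|
| 0.5 cm | >1.5 to 3.5 | >1.5 to 2 | >3.5 to 4 |
| 1 cm | >1 to 3 | >1 to 2 | >3 to 4 |

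Examples at s = 1 cm: a true 1.5 cm reads 2.5 cm and passes; a true 3.5 cm reads 4.5 cm and fails.

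**Shares, if true axial heights are spread evenly (assumption)**

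- s = 0.5 cm: 0.5 / 2 = 25% of those reading as eligible are truly 2 cm or less.
- s = 1 cm: 1 / 2 = 50%.
- The same shares of true >2 to 4 cm hernias in permitted Barrett's patients are wrongly excluded (0.5 / 2 and 1 / 2).

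**Patients, if 5-15% of those enrolled have permitted Barrett's (assumption)**

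- 50 × 0.05 = 2.5 and 50 × 0.15 = 7.5 patients.
- s = 0.5 cm: 0.25 × 2.5 = 0.6 to 0.25 × 7.5 = 1.9 wrongly admitted.
- s = 1 cm: 0.50 × 2.5 = 1.3 to 0.50 × 7.5 = 3.8 wrongly admitted.

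These counts use the axial dimension alone and give every permitted Barrett's patient the same shift. They are upper figures for each s, because the transverse requirement of inclusion 6 removes any hernia that is 2 cm or less across.

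**Would it matter to the primary test?** As a deliberately adverse illustration, let true >2 to 4 cm patients normalize at 24% and misread patients at 44%. With misread fraction f the overall rate is 0.24 + 0.20f, and P(X ≥ 18) is:

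| s | f | Misread of 50 | Chance of declaring non-inferiority |
|---|---|---|---|
| none | 0 | 0 | 0.038 |
| 0.5 cm | 0.0125 to 0.0375 | 0.6 to 1.9 | 0.042 to 0.051 |
| 1 cm | 0.025 to 0.075 | 1.3 to 3.8 | 0.046 to 0.065 |

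If misread patients normalize at the same rate as the others, the effect is nil.

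**The case against.** The strongest reply is that inclusion 6 already protects the window. It requires the transverse dimension as well as the axial height to be >2 to 4 cm, and a displaced Z-line does not touch the transverse dimension. A hernia of 2 cm or less both ways still fails, however high the Z-line sits. This stands, and it limits wrongful entry to hernias with axial height of 2 cm or less and a transverse dimension above 2 cm. It is only a partial safeguard, because 8.3 gives no method for the transverse measurement and it does nothing for large hernias misread as over 4 cm.

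Second, 1 cm is the ceiling on circumferential displacement when C above 1 alone excludes, not a typical value. With tongues only, most of the Z-line is not displaced, and the reading depends on which point the endoscopist takes. This also stands. The permitted 3 cm of M length should not be read as a 3 cm shift.

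Third, a reader might infer that letting in smaller hernias tilts the comparison with RESPECT toward success. The documents do not support that. The misread patients all have Barrett's, and nothing in the protocol says they normalize acid exposure more readily. The sample size section assumes the same 44% for HEURISTIC as for RESPECT. The 24% versus 44% contrast above shows the possible scale only.

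Fourth, the protocol does not say how the historical group with hernias of 2 cm or less was measured. If that was also from the Z-line, changing the landmark here alone would make the 2 cm boundary less comparable. This is a fair caution and shapes the fix.

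**Conclusion.** The point holds in a limited form. Following 8.3 as written over-reads axial hernia height in patients with a permitted circumferential Barrett's segment, and nothing in the plan corrects it. The error can admit hernias that are axially 2 cm or less but wider than 2 cm, and can exclude true hernias of >3 to 4 cm at a 1 cm shift.

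The size is small and uncertain: at most about 0.6-1.9 of 50 patients wrongly admitted at 0.5 cm and 1.3-3.8 at 1 cm, before the transverse requirement. This rests on an assumed 5-15% prevalence, an even spread of true sizes and a common shift. Reading exclusion 6 as requiring both limits to be exceeded would permit larger shifts.

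The point should not be taken to mean that any hernia of 2 cm or less can enter, or that the RESPECT comparison is biased in a known direction. The primary endpoint, N = 50, the 18/50 cut-off and the stated power are unaffected. This is a cheap improvement to a measurement definition.

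**What to change.** In section 8.3, define axial hernia size as the distance from the gastroesophageal junction, taken as the top of the gastric folds, to the diaphragmatic impression. When a columnar segment is present, record the Z-line position and Prague C and M separately. Use the same landmark at the 6-month EGD. While editing, state how the transverse dimension in inclusion 6 is measured, and whether the C and M limits in exclusion 6 are joined by *and* or *or*.

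The landmark change costs one sentence and one CRF field at endoscopies already in Table 4; the two clarifications are wording only. Applying the Prague limits already requires the endoscopist to locate the junction, so no new skill is needed. There are two downsides. The top of the folds is slightly harder to read in some patients, and the historical group may have been sized from the Z-line. Keeping the recorded Z-line distance preserves that comparison.

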8.4. BRAVO pH Studies

Acid reflux (off all antisecretory compounds for a minimum of 7 days) will be documented using pH-metry techniques utilizing BRAVO system. The BRAVO system will be used both at baseline/screening and at 6 months post procedure to document in a consistent way, across all sites for an ambulatory 48 hour pH.

Normal pH will be considered if pH < 4 lasts for $\leq 5.3\%$ of the time in a 48-hour monitoring period.

8.5. Esophageal Motility

- Measures LES resting pressure following standard protocol
- $> 50\%$ peristalsis with $> 30\%$ distal amplitudes
- 10 consecutive water swallows allows the assessment of propulsive motor function of the esophagus
- High-resolution motility is optional

9. Study Procedures

The schedule of observations and assessments to take place during the study follows on the next page. (**Table 4**)

Table 4. Study Events Schedule

	Initial Screening	Final Screening	Procedure	Post-Procedure/ Hospital Discharge	2-Week ±3 days	3-Month ± 15days	6-Month ± 20 days	12 and 24 Months ± 20 days
Inclusion/Exclusion Criteria	X	X						
Sign Informed Consent Form		X						
Demographics and Medical History	X							
Physical examination	X			X				
Record concomitant medications	X	X	X	X	X	X	X	
Recording of GERD Medications	X				X	X	X	X
Recording of duration of GERD Symptoms	X				X	X	X	X
Recording of type of GERD Symptoms	X				X	X	X	X
Recording of PPI Use; except for 2-week and 3-month visits, discontinue PPI usage for 7 days to evaluate study endpoints	X			X	X	X	X	X
RDQ, atypical symptom RSI, Quality of Life questionnaires GSRS, HRQL after being off PPI for at least 7 days	X						X	X
Discontinuation of anticoagulants if applicable (at least 10 days before scheduled TIF)	X							
EGD with optional biopsy		X					X	
Motility studies (High resolution optional)		X						
BRAVO pH study (at least 7 days after stopping all antisecretory compounds)		X					X	
Study Enrollment		X						
Hiatal Hernia Repair			X					
TIF 2.0 Procedure (if Hiatal Hernia successfully repaired with at least 2 cm of intra-abdominal esophagus)			X					
Adverse Event Reporting			X	X	X	X	X	

9.1. *Determination of Patient Eligibility – Screening Process*

Initial Screening -

The following pre-procedure data must be collected in order to determine patient eligibility:

- Demographics and medical history, to include age, weight, gender, and race
- Usage of GERD medication (medication, dosage, frequency and duration)
- Duration of GERD symptoms
- Type of GERD symptoms
- Duration of PPI Use
- Clinical symptom assessments (RDQ) and Quality of Life questionnaires (GSRS, HRQL, Atypical Symptom RSI)
- All general inclusion/exclusion criteria have been met

Upon completion of the Initial Screening Process, if it is determined that the patient does not have “troublesome” symptoms while on PPIs, they are **NOT eligible** for the study

Final Screening :-

The following pre-procedure data must be collected in order to determine eligibility:

- Informed consent signing
- Physical Examination
- Days since last PPI intake (prior to BRAVO pH study)
- EGD with optional biopsy
- High resolution motility studies (optional)
- Upper GI endoscopy
- Bravo pH studies (48 hours)

Patients who have met all entry criteria are enrolled to the study.

9.2. *Prior to the Study Procedure*

- The usage of any anticoagulants will be discontinued before TIF for at least 10 days.
- 12-hours before the procedure, the patient is expected to be fasting.
- Immediately before the procedure, each patient will undergo an endoscopic examination of the stomach and esophagus.

9.3. *During the Study Procedure*

A Transoral Incisionless Fundoplication will be performed following the standard laparoscopic Hiatal Hernia Repair and closure of the diaphragmatic defect (crura closure will be made

posterior with 2-3 separate stitches). The patient will be terminated from the study if hiatal hernia cannot be repaired, with at least 2 cm intra-abdominal esophageal length.

TIF Procedure (Treatment)

The TIF procedure (treatment) will be conducted under continuous visualization following a standard TIF2.0 protocol (**Figures 8**).

[figure not shown]

Figure 8. Standard TIF2 protocol

The usage of any anticoagulants will be discontinued before HHR and TIF 2.0 for at least 10 days. Patients are expected to fast for 12 hours before the procedure. Antibiotic prophylaxis will be administered during induction of general anesthesia (oro-tracheal intubation and anti-emetic protocol; dehydrobenzoperidol, dexamethasone, Zofran, Primperan).

As stated in Section 10.2, immediately before the procedure, each patient will undergo an endoscopic examination of the stomach and esophagus. The EsophyX ZR will be inserted transorally through a bite-block into the esophagus with the patient in either in supine, or 45 degrees or left lateral position.

During a single insertion of the device, a valve similar to that created through antireflux surgery will be reconstructed by retraction of full-thickness plications and tailored placement of multiple fasteners circumferentially 1-3 cm above the Z-line. The procedure is expected to last for 30-45 minutes. The quality of the

created valve will be evaluated by an endoscopic examination immediately after the procedure. Any complications related to the procedure will be recorded.

In the event of patient complaint of significant unmanaged GERD symptoms 14 days post procedure, the patient will be offered continued PPI therapy. (See below)

9.4. *Post-Procedure / Hospital Discharge*

Patients will be released the next day after a complete physical examination and instructed to consume a liquid diet during the first two weeks and a soft diet during the following four weeks. The liquid diet will consist of strained soups, pudding, milk, gelatin, yogurt, well-cooked and puréed vegetables, and chewable multivitamins. During weeks 3 to 6, patients will introduce a soft diet consisting of moist fish, canned fruits, bananas, berries, soft eggs, cooked vegetables, mashed potatoes, pasta, moist rice, and cereals (softened in milk). After the six-week healing time, patients can then incorporate fresh vegetables, meats, bread, citrus and alcohol back into their diet.

The usage of PPIs will be continued for 14 days following the procedure to allow healing of the gastric mucosa around the fasteners and to reduce patients' post procedure anxiety. In the event of the recurrence of troublesome symptoms, patients will be encouraged to contact the study coordinator. The nature, intensity and frequency of these symptoms will be assessed during in-office visits.

The designated staff at the clinical site will review the study requirements with the patient to maximize compliance with the follow-up schedule and the required medication regimen. Patients will be instructed to return for follow-up assessments according to the study event schedule in Section 8. A date for the follow-up visit (office or phone as appropriate) should be established between the patient and Investigator, and if possible the visits scheduled at the time of hospital discharge.

9.5. *Follow-up*

All enrolled patients will be evaluated at 2-weeks, 3-, 6-, and 12-Months and 24 months post TIF- procedure.

The study will be considered complete (with regard to the primary endpoint) after all patients have completed the 6-Month follow-up period.

Consultations may become necessary if major reflux symptoms emerge. Before each follow up time point the patient will be contacted by telephone in order to enhance clinical assessments and data compliance. Refer to the Schedule of Events (**Table 4**) for a comprehensive outline of protocol requirements.

10. Statistical Considerations

10.1. *Analysis Populations and Missing Data Handling*

Effectiveness Population - Per the Intent-to-Treat principle, all enrolled patients who receive the protocol TIF 2.0 procedure will be included in the effectiveness analysis.

Safety Population - Safety analysis will include all enrolled patients who receive any portion of the protocol required Hiatal Hernia Repair or TIF 2.0 procedures.

Missing data: All analyses will be based on available data. Missing data will not be imputed by methods.

10.2. *Statistical Analysis Plan*

